Lab Visit 3: Participants will undergo a urine screening for opiate use (females will also be screened for pregnancy); 5 minutes of seated rest; participants rate their current low back pain intensity; nurse inserts i.v. cannula; nurse administers randomized drug dose #1. Administration of randomized drug dose #1 will be followed by 10 minutes of seated rest to achieve peak drug levels; participant rating of chronic pain intensity; thermal pain task #1; assess thermal pain intensity; assess drug side effects and psychoactive effects; nurse administers randomized drug dose #2. Administration of drug dose #2 will be followed by 10 minutes of seated rest to achieve peak drug levels; participant rating of chronic pain intensity; thermal pain task #2; assess thermal pain intensity; assess drug side effects and psychoactive effects; nurse administers randomized drug dose #3 . Administration of drug dose #3 will be followed by 10 minutes of seated rest to achieve peak drug levels; participant rating of chronic pain intensity; thermal pain task #3; assess thermal pain intensity; assess drug side effects and psychoactive effects; nurse administers randomized drug dose #4. Administration of drug dose #4 will be followed by 10 minutes of seated rest to achieve peak drug levels; participant rating of chronic pain intensity; thermal pain task #4; assess thermal pain intensity; assess drug side effects and psychoactive effects; seated rest until side effects remit.

Exercise Manipulation (Weeks 4 – 10 of study participation): Following the third laboratory visit, participants will be randomly assigned to study condition, stratified by recruitment source (clinic vs. community). Participants randomly assigned to the exercise condition will then complete the 18 session aerobic exercise manipulation supervised by an ACSM-certified personal trainer at the Dayani Center (3 exercise sessions per week for 6 weeks). Participants assigned to the control condition will not undergo any manipulation during this 6 week period, and will be asked to continue their current activity levels and not engage in any additional exercise activity during the study period (confirmed via electronic diary). All subjects will complete brief pain and psychosocial questionnaires once weekly by phone.

Lab Visits 4 – 6 (\approx Weeks 11-12): Identical procedures to those described above for Lab Visits 1-3. Drug order is again randomized and counterbalanced.

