Post-Manipulation 5 day Electronic Diary Monitoring Period (\approx Week 11, between Lab Visits 4-5): Identical to pre-manipulation electronic diary procedures described above.

Description of Laboratory Visit Procedures:

All laboratory procedures will be conducted with participants seated upright in a comfortable chair. Each participant's series of three laboratory sessions (placebo, naloxone, morphine) carried out both pre- and post-manipulation will be scheduled within an ≈ 10 day period, at the same time of day to control for variance due to circadian rhythms.

Study Drug Protocol: Study drugs will be administered (in double-blind fashion) in randomized, counter-balanced order. The assigned study drug will be administered within a given session over 4 infusions (2 min each) according to the following protocol, depending on the assigned drug for that visit: 1) 4 doses of saline placebo (20ml each), 2) an 8mg dose of naloxone (in 20ml saline vehicle), followed by saline, 4mg naloxone, and saline, or 3) morphine sulfate (0.03 mg/kg in 20ml saline vehicle initially, followed by 3 incremental doses of 0.02mg/kg each). To avoid excessive morphine doses (and increased side effect risks) for individuals who are obese, a modified weight adjustment will be employed for individuals more than 30% over ideal body weight based on subjects' observed weight in clinic compared to appropriate ideal body weight for males (50kg+2.3kg for each inch over 5 feet) or females (45.5kg +2.3kg for each inch over 5 feet) [from <http://www.globalrph.com/>]. For individuals meeting this obesity criterion, morphine dosage will be based on Adjusted Body Weight rather than actual body weight, as calculated by: $\text{Ideal Body Weight} + 0.4 (\text{actual weight} - \text{Ideal Body Weight})$.

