Effect sizes ranged from $d=.6$ to $d=1.2$ in directions indicating that opioid blockade reduced post-exercise analgesia, suggesting that EO function partly mediated the effect of acute exercise on pain intensity. The mean effect size across these studies for the impact of EO mechanisms on exercise-related analgesia was $d= .93$ (equivalent to $r=0.42$). This effect size is key to initial analyses of Specific Aim 1. The proposed sample size will result in a power exceeding 0.90 for testing effects of the exercise manipulation on EO function (two-sided $p<.05$ significance criterion). Effect size estimates for the b path in the mediational model reflecting influences of EO function on morphine responses can be derived from our prior work, which indicated an average effect size of $r=0.27$ for associations between natural variations in EO function (opioid blockade effects) and analgesic responses to a single morphine dose across all pain measures and both laboratory evoked pain tasks¹⁸. Effect size for the b path reflecting influences of EO function on chronic back pain intensity can be estimated from Bruehl et al.²⁵, with an effect size of $r=0.26$ for associations between EO analgesic function in the laboratory and diary ratings of chronic back pain intensity (greater EO function was associated with lower daily back pain intensity). Given these effect sizes for the a and b paths in the mediation model, the total sample size for the proposed project was selected as $n=116$, resulting in a power of 0.80 (two-tailed $p<.05$ criterion for significance) for testing mediation effects hypothesized in Aims 1-3 using the proposed bootstrap approach (based on Fritz and MacKinnon⁶⁴).

Data Reduction and Analyses

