Blockade effect variables reflecting EO function will be derived by subtracting evoked pain responses during placebo from comparable responses during opioid blockade (separately for pre-manipulation baseline [BL] and post-manipulation). Given no theoretical rationale for expecting dose response effects with repeated dosing for placebo or naloxone conditions, we will average over the 4 pain stimuli within each of these drug conditions (separately for pre- and post-manipulation sessions) as a means of reducing random measurement error in deriving blockade effects. Blockade effects will be derived such that larger positive values reflect greater EO analgesia. To reduce number of variables, a mean value of the standardized EO function variables (blockade effects) will be derived and will be used initially in analyses (as in Bruehl et al.¹⁸). Chronic pain intensity pre- and post-manipulation will be defined as mean chronic pain ratings during the respective electronic diary sampling periods. As manipulation checks, we will determine whether degree of spontaneous EO function pre-manipulation is correlated significantly with evoked pain sensitivity and chronic pain intensity at BL. Total number of exercise minutes recorded during the post-intervention diary monitoring period (obtained in both groups) will be explored as a potential covariate for use in primary group analyses.

Primary Analyses.

Aim 1: To determine whether an aerobic exercise manipulation increases EO activity in CLBP patients, and whether these EO changes mediate manipulation-induced reductions in evoked pain responsiveness and daily CP intensity. We will conduct Group (exercise, control) x Time (BL, post-manipulation) mixed design ANOVAs to determine whether evoked pain sensitivity and CP intensity decreased significantly in the aerobic exercise group only. We will also conduct Group (exercise, control) x Time (BL, post-manipulation) mixed design ANOVAs on EO function (blockade effect variables pre- and

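### Exercise minutes recorded after randomisation may enter the primary group tests as a covariate, with no entry rule or model form

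*Combined protocol and SAP*

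**What the plan says.** The covariate appears in Section 10.0, Data Reduction and Analyses: "Total number of exercise minutes recorded during the post-intervention diary monitoring period (obtained in both groups) will be explored as a potential covariate". The sentence goes on to name the primary group analyses as the place of use. Nothing in the document says when the variable would be kept, whether it enters as a main effect or with a time interaction, which outcomes it applies to, or whether the unadjusted result stays primary.

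The primary models are written without covariates. For Aim 1: "We will conduct Group (exercise, control) x Time (BL, post-manipulation) mixed design ANOVAs". Aims 2 and 3 follow the same pattern.

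The timing is in Section 6.0. On randomisation: "Following the third laboratory visit, participants will be randomly assigned to study condition". The post-manipulation diary is placed at about "Week 11, between Lab Visits 4-5): Identical to pre-manipulation electronic diary procedures described above". In between, one arm trains under supervision three times a week for six weeks, while controls are asked to keep their current activity and "not engage in any additional exercise activity during the study period".

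Under Aims 1 and 2 in Section 10.0, a significant effect of exercise on an outcome is the only precondition for testing mediation of that outcome.

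**The concern.** Exercise minutes in Week 11 are a post-randomisation variable. Assignment can affect them: controls are asked not to add exercise, and the other arm has just finished a training programme. They may also be related to outcome. For chronic pain intensity, the outcome comes from the same five-day diary, so pain could influence exercise as well as the reverse.

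Adjusting a randomised comparison for such a variable can change the question being answered. The adjusted Group x Time term compares arms at equal post-intervention exercise, which is not the effect of being assigned to exercise. The direction is not fixed. The shift is toward no effect if the exercise arm records more minutes and more minutes go with more improvement. It is toward apparent benefit if exactly one of those signs is reversed, for example if more exercise goes with more soreness.

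The trial is powered for mediation, and mediation is tested only after a significant group effect. The documents do not say that an adjusted test would serve as that precondition. If it did, mediation tests could be wrongly skipped or wrongly run. With no entry rule, a choice between adjusted and unadjusted results after seeing the data adds a smaller error of its own.

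**Working it through.** **Inputs from the documents.** N = 116 (Section 10.0), half assigned to exercise (Section 7.0), so 58 per arm; two-sided 0.05. Section 10.0 gives a mean d of 0.93 and says: "Effect sizes ranged from $d=.6$ to $d=1.2$ in directions indicating that opioid blockade reduced post-exercise analgesia". These values concern endogenous opioid (EO) effects after acute exercise in healthy people. They serve here only as reference effect sizes.

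**The plan's own figures reproduce.** d = 0.93 converts to r = 0.93/√(0.93² + 4) = 0.42. Power for the group effect with 58 per arm is 0.999 at d = 0.93, consistent with the stated value above 0.90, and 0.893 at d = 0.6 (noncentral t). Simulated bias-corrected bootstrap power for mediation with a = 0.42 is 0.80 at b = 0.26 and 0.81 at b = 0.27, against the stated 0.80. The sample size is not in question.

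**Model form.** With two time points, Group x Time is the arm difference in change, and a covariate with one value per person cancels from the change unless it interacts with time. In 200 simulated two-time-point mixed models (d = 0.93, arm gap 1.0 SD, correlation 0.25), adding minutes as a main effect moved the Group x Time estimate by less than 1e-14. Adding minutes x Time moved it by -0.246 on average (expected -0.25).

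**Size, with assumed inputs.** The documents give neither the arm gap in minutes, Δ (within-arm SD units), nor rho, the within-arm correlation of minutes with change. Assumed: Δ = 0.5 or 1.0, rho = 0.16 or 0.25. With g = 0 or 1 for arm, the generating model is:

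- minutes Z = Δ·g + Z0
- change = d·g + rho·Z0 + √(1 − rho²)·e

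Here d is the total effect of assignment, positive favouring exercise. The expected adjusted estimate is d − rho·Δ. Example: 0.6 − 0.25 × 1.0 = 0.35.

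Results from 40,000 simulated trials per cell (simulation SE at most 0.0025):

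| Δ | rho | d = 0.93 becomes (power) | d = 0.6 becomes (power) | Rejection at d = 0 |
|---|---|---|---|---|
| 0.5 | 0.16 | 0.85 (0.993) | 0.52 (0.779) | 0.071 |
| 1.0 | 0.16 | 0.77 (0.958) | 0.44 (0.566) | 0.118 |
| 0.5 | 0.25 | 0.805 (0.991) | 0.475 (0.711) | 0.105 |
| 1.0 | 0.25 | 0.68 (0.913) | 0.35 (0.405) | 0.235 |

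Hand check of the last row: the variance of the adjusted estimate is about (1 − 0.25²) × (2/58 + 1.0²/114) = 0.9375 × 0.0433 = 0.0406, so SE = 0.201. For d = 0.6, 0.35/0.201 = 1.74, and power is about Φ(1.74 − 1.98) = 0.41, in agreement.

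**Direction under the null.** With positive rho, nearly all the rejections at d = 0 go against exercise (0.062, 0.114, 0.100 and 0.234 in row order). With the sign of rho reversed they favour exercise at 0.062, 0.120, 0.099 and 0.234, against a nominal 0.025.

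**Choosing after seeing the data.** Taking the smaller of the adjusted and unadjusted p-values at d = 0, with rho = 0, 0.16 and 0.25:

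- Δ = 0: 0.053, 0.058, 0.064
- Δ = 0.5: 0.061, 0.088, 0.126
- Δ = 1.0: 0.070, 0.142, 0.259

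**No-bias cases.** With rho = 0, d stays at 0.93 (power 0.998 at Δ = 0.5 and 0.992 at Δ = 1.0). With no arm gap the estimate is also unchanged. A main-effect-only term leaves the test identical.

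**The case against.** The plan does not commit to this adjustment: the variable is only to be "explored as a potential covariate for use in primary group analyses", and every confirmatory model is written as a plain Group x Time ANOVA. Harm needs the option to be taken and then three further conditions, none of which the documents establish. Supervised training has ended by Week 11, the documents do not say that the exercise arm keeps training, and both arms were screened as inactive, so the arm gap could be small. At d = 0.93, power stays above 0.90 in every cell above. The large losses need the lowest d together with a large assumed gap. The null rejection rates also depend on how minutes and change are linked. With d = 0, the generating model implies either an unmeasured cause shared by minutes and change, or a direct effect of assignment that exactly cancels the effect through minutes. In the second case the adjusted test is correctly testing something other than the effect of assignment.

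Most of this stands as a limit on size: the option may never be used, the gap and rho are guesses, and an adjusted precondition for mediation is speculative. It does not remove the point. The text places the variable in the primary analyses and nothing keeps the unadjusted test primary. The form that does no harm leaves Group x Time untouched, so the covariate can influence that test only in a form that can bias it. The null rates are errors with respect to the effect of assignment, which is the effect randomisation identifies and the plan sets out to test.

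**Conclusion.** The concern holds as a conditional one. As written, the plan allows a post-randomisation variable that assignment can affect into the primary group tests, with no entry rule or model form. If it enters with a Covariate x Time term or in a change-score model, differs by arm, and correlates with change within arm, the test is shifted from the effect of assignment by about −rho·Δ in SD units. Over the assumed range that is 0.08 (0.16 × 0.5) to 0.25 (0.25 × 1.0) SD. This matters little for power at d = 0.93 and substantially at d = 0.6. Confidence that the wording leaves this open is good. Confidence in the size is low, because both driving quantities are assumed. The plan should be changed on this point, but it is an open option to close and not an error in a specified analysis.

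**What to change.** State in Section 10.0 that the primary Group x Time analyses, and the group test that is the precondition for mediation, do not include post-intervention exercise minutes. Report those minutes by arm as a check on compliance and contamination (Section 6.0 already uses the diary to confirm that controls add no exercise), or use them only in a model labelled exploratory. If adjustment for activity is wanted, pre-specify a measure taken before randomisation that is already collected, together with the model form. The candidates are the International Physical Activity Questionnaire at screening (Section 6.0) and the pre-manipulation diary exercise items (Section 4.0).

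The cost is one or two sentences. No new data are needed, and N = 116 and the stated power are unchanged.

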5.0 Enrollment/Randomization

Participants will be recruited from a list of potentially qualifying participants from past studies in our lab who had previously indicated a desire to be contacted about future studies, as well as via local newspaper advertising, posted flyers (including at the Vanderbilt Interventional Pain Center and the Osher Center for Integrative Medicine at Vanderbilt), and e-mail advertisements distributed throughout campus via the Vanderbilt mass e-mail system. Interested individuals will be able to contact the designated study research assistant by phone or e-mail. Random assignment to both study conditions will be stratified by community vs. clinic population recruitment source to control for possible influence of this variable on results. Approximately equal numbers of males and females of all races will be recruited for the study. Individuals expressing an interest will first be provided verbally with information on the study procedures, risks, and benefits, and if interested, will be given the opportunity to read the IRB-approved informed consent form. All questions from potential subjects will be answered by the study representative as accurately as possible. All individuals agreeing to participate will provide written informed consent prior to beginning any study procedures. Subject recruitment and consent procedures will be carried out by individuals designated and trained by the PIs and the IRB to carry out these procedures (i.e., the research assistant).

The study will employ a mixed between/within-subjects design using double-blind, counterbalanced, placebo-controlled administration of both an opioid antagonist (naloxone) and an opioid agonist (morphine). The study will use a 6 week supervised aerobic exercise manipulation, with subjects randomly assigned to the exercise protocol or a no exercise control condition. All participants will undergo three identical laboratory pain-induction sessions (each \approx 5 days apart) prior to randomization to experimental condition, and again at the end of the 6 week exercise manipulation period (regardless of exercise group assignment) during which they will receive the 3 study drugs and participate in controlled laboratory evaluation of evoked thermal pain responsiveness.

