Exercise Manipulation Protocol: Participants randomly assigned to the exercise training group will undergo aerobic exercise training 3 times/wk for 6 wks. To enhance and monitor adherence, all of the exercise sessions will be conducted at the Dayani Center and supervised by ACSM certified personal trainers thoroughly trained in study procedures. Each exercise session will consist of a 5 minute warm-up, 30 minutes of aerobic exercise, followed by a 5 minute cool-down period. Aerobic exercise will consist of treadmill walking/running, stepping, elliptical, or cycling exercise as preferred by the participant. This will allow participants to choose the type of aerobic exercise most tolerable to them to minimize symptom exacerbation (i.e., acute increases in pain) while maximizing adherence to the training program. Effort levels across the different types of aerobic exercise will be standardized using heart rate (HR) and perceived exertion (RPE) monitoring as recommended by the American College of Sports Medicine (ACSM). Target heart rate zones will be established using the Karvonen formula and heart rate reserve (HRR). Duration of exercise will be standardized at 30 minutes with a target exercise intensity between 70-85% HRR (RPE = 15, hard). Because of the focus on de-conditioned individuals with CLBP, the duration and intensity of exercise will be progressively increased up to target during the first two weeks to avoid symptom exacerbation and minimize study drop-out. Participants will begin with 10-15 minutes of exercise between 40-55% HRR (RPE = 11-12, light) during the first week, 20-30 minutes of exercise between 55-70% HRR (RPE = 12-13, somewhat hard) during the second week, and then 30 minutes of exercise between 70-85% HRR (RPE= 14-16, hard) for the duration of the study. To ensure that participants are exercising within their prescribed workload during each session, HR and RPE will be assessed and recorded every 5 minutes during exercise using Polar HR monitors and Borg's 6-20 RPE scale. In addition, pain will be assessed every 5 minutes during exercise using a pain rating scale developed for this purpose to monitor back pain, with adjustments to the workload in the event of back pain during exercise.

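### The Aim 1 chronic-pain ANOVA, as usually run, uses only participants with a week-11 diary and leaves the weekly phone pain data unused; unequal pain-related drop-out could bias it either way

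*Combined protocol and SAP*

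**What the plan says.** - **Outcome.** Section 10.0, Data Reduction and Analyses: "Chronic pain intensity pre- and post-manipulation will be defined as mean chronic pain ratings during the respective electronic diary sampling periods". Section 6.0 places the "Post-Manipulation 5 day Electronic Diary Monitoring Period" at about week 11, between Lab Visits 4 and 5.
- **Test.** Section 10.0, Aim 1, uses Group x Time "mixed design ANOVAs to determine whether evoked pain sensitivity and CP intensity decreased significantly in the aerobic exercise group only", with two time points, baseline and post-manipulation.
- **Missing data.** Section 10.0 contains no missing-data rule, analysis set, intention-to-treat statement or sensitivity analysis. Section 9.0 allows withdrawal at any time and describes no data collection afterwards.
- **Unused data.** Section 6.0, Exercise Manipulation: "All subjects will complete brief pain and psychosocial questionnaires once weekly by phone". This falls after randomisation and before Lab Visit 4, in both arms. No analysis in section 10.0 names these data.
- **Drop-out.** In section 6.0, Exercise Manipulation Protocol, training is "progressively increased up to target during the first two weeks to avoid symptom exacerbation and minimize study drop-out". Participants choose the type of exercise, and pain is monitored "with adjustments to the workload in the event of back pain during exercise".
- **Controls.** They "will be asked to continue their current activity levels and not engage in any additional exercise activity during the study period".
- **Return visits.** Section 5.0 has all participants undergo the lab sessions before randomisation and "again at the end of the 6 week exercise manipulation period (regardless of exercise group assignment").

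**The concern.** With two time points, the Group x Time interaction is a comparison of change scores between arms. A participant with no post-manipulation diary has no change score. Randomisation follows Lab Visit 3, so anyone lost during the six weeks is lost after randomisation, and the remaining comparison is no longer fully protected by it.

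Only one arm trains, so reasons for leaving may differ between arms. If more exercisers than controls leave with worsening pain, the remaining exercisers look better than the arm as randomised, and a benefit can appear that is not there. Controls could also leave because of pain: they enter with daily back pain and receive no intervention for six weeks. If more of them leave this way, a real benefit can be hidden.

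The chronic-pain group effect is also the precondition for the chronic-pain mediation test. Section 10.0 reads a significant direct path without a significant indirect path as a non-opioid mechanism, so a drop-out artefact could be given a mechanistic explanation.

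**Working it through.** **The plan's own figure.** The plan gives no drop-out figure to reproduce. Its sample-size figure is not in dispute: simulating the bias-corrected bootstrap at n=116 with a=0.42 and b=0.26 gives power 0.795, against the stated 0.80.

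**Inputs.** From the documents: 116 participants (section 10.0), half assigned to exercise (section 7.0), hence 58 per arm if all 116 are randomised; two-sided 0.05, hence 2.5% in each direction. Assumed, because the documents are silent: true effect zero; loss pE in exercise and pC in control; leavers' change worse than stayers' by delta, in SDs of the change score.

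**Formula.** If an arm's full mean change is zero, its stayers average -p x delta. The completer contrast is therefore biased toward exercise by (pE - pC) x delta. With n = 58 x (1 - p), rounded, the noncentrality is bias / sqrt(1/n1 + 1/n2). The false favourable rate is the noncentral t tail beyond the two-sided 0.05 cut.

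**Example.** pE = 20%, pC = 0, delta = 0.5: bias = 0.20 x 0.5 = 0.10 SD; n = 46 and 58; standard error = sqrt(1/46 + 1/58) = 0.197; noncentrality = 0.10/0.197 = 0.51; cut 1.983 on 102 df; rate 7.2%.

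**False favourable rate (nominal 2.5%)**

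| Leavers worse by | Control loss | Exercise loss 10% | 20% | 30% |
|---|---|---|---|---|
| 0.25 SD | 0 | 3.4% | 4.4% | 5.5% |
| 0.5 SD | 0 | 4.5% | 7.2% | 10.9% |
| 0.5 SD | 10% | 2.5% | 4.3% | 6.9% |
| 1.0 SD | 0 | 7.5% | 16.9% | 30.7% |
| 1.0 SD | 10% | 2.5% | 7.1% | 15.6% |

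**Reverse case.** With 10% exercise loss, 20% control loss and delta = 1.0, bias = (0.10 - 0.20) x 1.0 = -0.10 SD: 0.7% of results falsely favour exercise and 7.1% falsely favour control.

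**Second model of drop-out.** A separate simulation took pain SD 2.0 points, with weekly drop-out more likely as pain rises.
- Pain-driven loss in exercise and random loss in control, 58 per arm: the false favourable rate was 5.8% at 10%/10% loss, 6.0 to 11.0% at 20%/10% and 9.1 to 19.8% at 30%/10%.
- Pain-driven loss in both arms: completer bias was -0.04 to -0.31 points when exercise loss was higher, and about zero when rate and mechanism matched.

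Equal loss is therefore harmless only if the reasons for leaving are also alike.

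**Would the phone data help?** A third simulation used exercise-only loss of 10 to 30%, six phone scores equal to true pain plus noise (SD 0.7), and multiple imputation. Its unit is the diary SD, not the change-score SD, so its figures are not on the table's scale.
- Leaving driven by recorded phone pain: completer bias -0.08 to -0.26; after imputation at most 0.018 in size.
- Leaving driven by later, unreported pain: completer bias -0.11 to -0.36; after imputation -0.04 to -0.18, so 35 to 52% of the bias remains.

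**The case against.** **The exclusion is inferred.** A reader might take the plan to say that participants without a week-11 diary are dropped. It does not. The exclusion follows from a two-point ANOVA with no other handling stated. A partly completed diary still gives a mean, so only a wholly missing one matters. This stands, but leaves the method unable to use someone with no final diary.

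**The direction is unknown.** A reader might infer that the protocol predicts drop-out from training, and so bias toward exercise. The text names avoiding exacerbation and limiting drop-out as two aims of a safeguard. It does not say that one causes the other and gives no rate. Supervision, choice of exercise and workload adjustment all lower the risk. This stands in full, and is why the point is stated for both directions.

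**The sizes are assumed.** The 1.0 SD row with no control loss is a worst case. The second simulation's exercise-only biases correspond to leavers roughly 0.4 to 0.7 diary SD worse. This stands.

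**Everyone returns.** Section 5.0 expects all participants back for the post-manipulation lab sessions whatever their arm. It does not mention people who stop exercising, nor the diary, so it answers the concern only in part.

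**The phone instrument is unseen.** Its items, scale and recall period are not given, and people who withdraw may also stop answering calls. This stands as a limit on the fix.

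**Conclusion.** The point holds as a conditional weakness with a cheap improvement available. As usually run, the planned chronic-pain test uses only participants who supply a week-11 diary, although pain data collected after randomisation in both arms are already planned. If pain-related loss differs between arms, the result can be biased in either direction; if rate and worsening are equal, bias is about zero.

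Under exercise-only loss of 10 to 30% with leavers 0.5 change-score SD worse, the false favourable rate is about 4.5 to 11% against 2.5%; at 1.0 SD it is 7.5 to 31%. These rest on 58 randomised per arm, no true effect and assumed loss.

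A reader might extend this to a spurious finding on endogenous opioids (EO) or morphine. The documents do not support that. A false chronic-pain benefit would open only the chronic-pain mediation test, whose indirect-effect interval must still exclude zero. Evoked pain, EO function and morphine outcomes depend on Lab Visits 4-6 and could lose the same people, but no bias was computed for them.

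**What to change.** 1. For chronic pain, analyse all randomised participants as assigned, with a likelihood-based mixed model or multiple imputation. Use the baseline diary, the weekly phone pain ratings as auxiliary data, and the week-11 diary. Test the arm difference in change at week 11. Confirm that the phone items include a pain rating.
2. State that participants who stop exercising are still asked for the phone calls, the week-11 diary and Lab Visits 4-6. Only this part helps the evoked-pain, EO and morphine outcomes.
3. Add a sensitivity analysis that shifts leavers' missing change by 0.5 and 1.0 SD of the observed change score, in the exercise arm alone, the control arm alone and both arms.
4. Report leavers by arm and reason, with back pain as a separate reason.

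The cost is a few SAP sentences, modest extra analysis, and effort to keep contact with people who stop exercising; the weekly calls are already planned. The downside is reliance on unblinded phone self-report with unspecified items. Part 1 corrects only part of the bias if unreported pain drives leaving, which is why parts 2 and 3 are needed as well.
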